Randomisation	Randomisation of task order and monitor trend scenario: increasing/decreasing
Timing control task	To assess baseline time perception for each participant
Break	To reset and brief the participant for the first task
First task	Administrative or technical task depending on randomisation

Monitor scenario in first task	The parameters do not change aside from a brief desaturation at 30 seconds into the task, to orient participants to the monitor within the task
Break	To reset and brief the participant for the second task
Second task	Administrative or technical task depending on randomisation
Monitor scenario in second task	There is a desaturation at 30 seconds as before to orient participants to the monitor within the task. The blood pressure then either falls or rises, depending on the randomisation, settling at the final value at 4 minutes. The change in blood pressure only occurs in the second task so as to allow immediate review of trend awareness, this is not possible to do after the first task without introducing bias in the second task.
Post task review	To check immediate recall of monitor trends in the second task. Asked immediately to reduce the impact of recall/memory bias on the answers.
Questionnaire	Provides quantification of any trend in parameters noticed.
Debrief	To answer queries and identify any areas of participant support required.

Experimental scenarios:

Each participant will undertake the timing control task first and then both the administrative and technical tasks, the order of these determined by the randomisation table.

1. Timing control

The participant sits and is asked to push a foot pedal every 10 seconds with no reference to external timekeeping. This task continues for 6 minutes.

Participants are instructed: "Please press the foot pedal every 10 seconds, trying to be as accurate as possible. The task will last for several minutes."

After 6 minutes the participant will be asked for the time period they believe has elapsed between the first pedal press and the last.

2. Administrative task:

Request investigations for a new admission

Equipment required:

- PIMS-TS investigations pack
- Computer signed in to the EPIC learning environment for a dummy patient
- Simulated bedside monitor
 - Varies observations over time in line with preset programming determined by the study team
- Foot pedal and data recorder for time logging

Setup

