 - The blood pressure will fall from an initial systolic/diastolic (mean) of 90/50 (63) at 30 seconds to 75/48 (55) at 4 minutes and then remain static at that level. There will be no alarm. This gradual drift tests participants' awareness and identification of monitoring trends during the task through what point they notice a change, if they do at all.

- Other parameters (heart rate, respiratory rate, oxygen saturations, end-tidal CO₂ and temperature) will not vary.
- Scenario B
 - The oxygen saturation measure will fall to 88% for 5 seconds at 30 seconds into the task, triggering an alarm. This is to orient the participant to the monitor being part of the environment.
 - The blood pressure will rise from an initial systolic/diastolic (mean) of 75/48 (55) at 30 seconds to 90/50 (63) at 4 minutes and then remain static at that level. There will be no alarm. This gradual drift tests participants' awareness and identification of monitoring trends during the task through what point they notice a change, if they do at all.
 - Other parameters (heart rate, respiratory rate, oxygen saturations, end-tidal CO₂ and temperature) will not vary.

End point:

6 minutes or completion of the task.

The participant will be asked for the time period they believe has elapsed between the first pedal press and the last.

3. Technical task

Inserting a CVC.

Equipment required:

- Child mannequin, intubated
- CVC insertion mannequin
- US machine + gel + probe cover
- CVC set
- Syringes, flush
- Cleaning- chlorprep lollipops
- Suture, needle holders, scissors, sharps bin
- Dressings + biopatch
- Gloves (non-sterile)
- Drape
- 5 +10ml syringes
- Sterile field drape
- Pen and paper for documentation
- Simulated bedside monitor
 - Varies observations over time in line with preset programming determined by the study team
- Foot pedal and data recorder for time logging

Setup

All equipment laid out on a table. The tissue pad is attached to the mannequin leg and surgically draped appropriately. The ultrasound probe is already in a sterile sheath, lying on the sterile field.

Instructions to subject

You are the fellow/consultant looking after Sophie. Sophie is a 2 year old girl with PIMS-TS who requires central access for inotropes. She is intubated and is stable on minimal ventilation and peripheral noradrenaline of 0.1mcg/kg/min. This is the Sophie's bedspace, all the equipment you see is part of the simulation

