You have been asked to insert a femoral CVC and have already prepared your equipment.. The line is not flushed. You are already wearing the appropriate sterile gown. Please only use steristrips and dressings, with no sutures, to secure the line to the mannequin. Please document the procedure on the paper provided when you have completed insertion of the line.

I am the nurse in the next bedspace, if at any point you want to make a clinical intervention please continue with the task and verbalise anything you would like me to do.

As before, from when I ask you to begin, please press the foot pedal every 10 seconds, trying to be as accurate as possible. The task will last for several minutes.

Given that this is a simulated mannequin please take all the time you need to familiarise yourself with the ultrasound appearance of the vessels before telling me you are ready to begin.

Events during the task:

Same as for the administrative task.

End point

6 minutes or completion of task documentation.

At the end of the task, progress through the checkpoints below will be noted by the experimenter:

1. Equipment preparation / line flushing
2. Cleaning of the procedure site
3. Initial ultrasound scan
4. Needle manipulation
5. Guide wire insertion
6. Tract dilation
7. Line insertion
8. Line suturing
9. Line dressing
10. Documentation completed

The participant will be asked for the time period they believe has elapsed between the first pedal press and the last.

Post- task review

Following completion of the second task the participant will immediately be asked the following questions:

“Did you see anything of note on the monitor aside from the desaturation” - their yes/no answer is recorded.

“If there were changes in the blood pressure did you notice a fall or a rise” - their rise/fall answer is recorded.

Was the extent of the fall/rise in systolic pressure: 5, 10,15, 20 or 25 mmHg- their selection is recorded.

Which of the tasks did you find more challenging? And why?

They are then asked to describe their subjective experience- “how were those tasks for you?”

They are then asked- “How would you describe your familiarity with EPIC order requesting?”- Very, somewhat, limited, none

They are then provided with the questionnaire from the appendix.

Measurement tools used

- For each experimental run there are 2 variables
 - The task order- administrative or technical completed first

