 - The trend in monitored observations- increasing or decreasing blood pressure in the second task

The following parameters are measured during both tasks:

- Timestamps of foot pedal use by the participant
- Retrospective recall of total elapsed time
- Time to complete task/progress at experiment end
- Question responses

Following completion of the tasks the data collected can be analysed as below.

Time interval analysis:

- Intervals between pedal presses are extracted for each scenario (timing control/administrative/technical tasks)
 - Derive: min/max/mean/interquartile range/standard deviation for each case
- Comparison of the individual’s retrospective perceived elapsed time with actual elapsed time. Reported as percentage error of actual elapsed time.

This will allow the following results to be reported:

- Mean deviation for each individual from their baseline in each of the tasks.
- Change in retrospective perceived elapsed time compared to actual elapsed time.
- Distribution of timing in the control task for each individual.
- Paired t-test comparison to test if there are significant differences in time interval distribution for each individual between control, administrative and technical tasks.
- Overall proportion of participants showing significant deviation from their own baseline in each of the administrative and technical tasks
- Population limits/mean
- Comparison of the mean perceived time interval between subgroups
 - By task order

- By time within task (split into thirds- 2 minutes each)
- By grade
- By number of CVCs previously inserted
- By first 25% vs last 25% of participants

Monitor trend perception analysis:

Each participant will provide question answers from immediately after the second task.

This will allow the following results to be reported:

- Rationale
 - The first question “Did you see anything of note on the monitor” is chosen to highlight inattentive blindness and is asked immediately to avoid any impact from the role of memory or priming from other questions asked.
 - This will be reported as proportion who noted a change
 - The subsequent questions are asked to elicit responses from those who observed the trend but are not sufficiently confident in their recall to report it.
- From the responses the following can be derived:
 - Correct identification of the blood pressure trend- reported as proportion of participants correct

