 - Correct identification of no trends in other parameters - reported as proportion of participants correct
 - Accuracy of magnitude recall
 - The blood pressure either falls or rises between a systolic/diastolic (mean) of 70/48 (55) and 90/50 (65).
 - From the position of the x on the linear blood pressure scales we can derive:
 - The accuracy of the initial and final estimates compared with the actual values- reported for each task as the population mean and standard deviation of the percentage errors compared with the actual value.
 - The accuracy of the magnitude of the change, determined through comparing the difference in the estimated initial and final values compared with the actual 20mmHg systolic/ 10mmHg diastolic change for each task. The population mean and standard deviation of the percentage errors compared with the actual change will be reported for each task.
 - We hypothesised that there would be a priming effect following administration of the questionnaire, with participants more likely to attend to blood pressure trends if the questions were asked prior to the second task. We will therefore only ask the questions after the second task. We can then compare between the subgroups, split by which of the tasks was performed second to examine the impact of task type.
 - i.e the questionnaire analysis will have half the n of the overall study
- For the above we can compare subgroups using Fishers exact test.
 - By task order
 - By grade
 - By number of CVCs previously inserted

- By first 25% vs last 25% of participants

STATISTICAL CONSIDERATIONS AND DATA ANALYSIS

Sample size and statistical power

This is a pilot study and as such we do not expect it to be adequately powered to confirm hypotheses but intend that it should be hypothesis generating.

Statistical methods

The population summary statistics detailed above will be calculated using 'SPSS statistics' software with built-in min/max/mean/IQR/SD calculation.

With assumed normally distributed timing data and each participant completing 2 tasks the distributions will be compared with a paired sample t-test for; control vs administrative, control vs technical and administrative vs technical. For subgroup analysis paired or unpaired sample t-tests will be used as appropriate in each case. For the trend perception outcomes, contingency tables will be created for each subgroup and compared using Fishers exact test.

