Given the relatively small sample size we will test the assumption of normal distribution with the Shapiro-Wilk test, run through SPSS.

ETHICAL CONSIDERATIONS

The study will only collect anonymised data relevant to the tasks and the participants' grade/seniority at work. No sensitive data will be collected. No identifiable personal data will be collected. Data collected will be stored on a password protected NHS computer. No data will be passed to other data processors. No participants will be recruited from vulnerable groups. No personal data will be retained and experimental data will be retained for 7 years electronically, with the paper questionnaires scanned and the physical copies destroyed.

Participants will be provided with the information sheet appended and given the opportunity to ask any questions before consenting to the study. They will be asked to sign the appended consent form. Their consent forms will be in no way linked to the data collected such that participants could be identified from their data.

Safety considerations/Patient safety

The study will be undertaken in a simulation room frequently used for similar tasks and training. This is a safe environment in the hospital, following current occupational safety and fire legislation.

The most likely risk is of a sharps injury given the use of needles and sutures. Sharps safety equipment for disposal is available, as is first aid equipment. Should an injury occur appropriate first aid will be undertaken. The event will also be recorded in the study notes as a high incidence of sharps injuries would prompt local training focus.

The risks of the study are:

- Sharps injury, rare in usual work or other simulation teaching tasks.
- Taking time away from clinical duties. The study is not mandatory and will only be run on days approved by the lead PICU consultant as being safe to do so.
- Additional pressure/stress on participants. There is already a mandatory CVC insertion training package which has been well received. The anonymity of performance outcomes should help minimise these concerns.

Participants regularly participate in simulation in the workplace and we do not expect that this study poses any more burden on participants than the simulation teaching programme. As in the simulation teaching programme, if unsafe practice is noted during the tasks this will be fed back sensitively to the individual with signposting to the CVC training package.

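### The share of participants counted as significantly off their own baseline has no known rate under no task effect, and the paired unit is not stated consistently

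*Combined protocol and SAP*

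**What the plan says.** Under Time interval analysis, intervals between pedal presses are extracted for the control, administrative and technical runs, and their mean, SD and other summaries are derived. The reported results include a "Paired t-test comparison to test if there are significant differences in time interval distribution for each individual between control, administrative and technical tasks" and, in the next bullet, the "Overall proportion of participants showing significant deviation from their own baseline in each of the administrative and technical tasks".

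Statistical methods gives a different basis for pairing: with "each participant completing 2 tasks the distributions will be compared with a paired sample t-test", three comparisons are made (control v administrative, control v technical, administrative v technical). The only assumption check is that "we will test the assumption of normal distribution with the Shapiro-Wilk test".

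Run lengths are set in the task descriptions. For control, "This task continues for 6 minutes". The administrative run ends at "6 minutes or completion of the task" and the technical run at "6 minutes or completion of task documentation". "Time to complete task/progress at experiment end" is among the measurements. Control is always done first; only the order of the two tasks is randomised. No significance level is stated.

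**The concern.** To call one participant significantly different from their own baseline, the analyst must test that person's task intervals against that person's control intervals. Two features of the data undermine such a test.

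- Successive presses by one person may be correlated. A t-test on them assumes they are not, and a normality test does not address this.
- Each condition is run once per person. If someone's pace varies from run to run for reasons unrelated to the task, the within-person test cannot separate that variation from a task effect.

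The usual benchmark, that about 5% are flagged when nothing is going on, therefore need not hold in either direction. Timing is a primary outcome, and Outcomes and Significance links impaired time perception in an individual to staffing and policy. A reader could take the count of significant individuals straight to that question.

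There is also a unit problem. The first bullet can mean pairing within a person, interval by interval, which the second bullet favours. It can also mean pairing by participant, which Statistical methods implies. Under the within-person reading, interval k of one run has no natural partner in another, and the counts differ because pace is self-set and tasks may end early.

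**Working it through.** The plan gives no expected proportion, significance level or sample size, so there is no figure to reproduce.

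**Inputs from the documents:** target interval 10 s; control run 6 minutes; task runs 6 minutes or to completion; one run per condition. At 10 s, 360/10 = 36 presses, or about k = 35 intervals.

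**Assumptions, not in the documents:** interval SD 2 s, two-sided 0.05, and the values of serial correlation ρ, run-to-run SD τ, slowing, early finish and drift used below.

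**1. Serial correlation, no task effect.** With first-order autocorrelation, the variance of a run mean is multiplied by about (1+ρ)/(1−ρ). The chance of being flagged is 2 × [1 − Φ(1.96/√((1+ρ)/(1−ρ)))]. The simulations used 40,000 to 100,000 participants per case, with intervals drawn to 360 s and a paired t-test in press order.

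| ρ | variance factor | formula | simulation |
|---|---|---|---|
| −0.3 | 0.54 | 0.8% | 0.9% |
| 0 | 1.00 | 5.0% | 4.8% |
| 0.1 | 1.22 | 7.6% | 7.3% |
| 0.3 | 1.86 | 15.0% | 14.7% |
| 0.5 | 3.00 | 25.8% | 25.5% |

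**2. Run-to-run variation, ρ = 0, no task effect.** The factor becomes 1 + kτ²/SD².

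| τ (s) | interval SD (s) | factor | formula | simulation |
|---|---|---|---|---|
| 0.25 | 2 | 1.55 | 11.5% | 10.8% |
| 0.5 | 2 | 3.19 | 27.2% | 25.4% |
| 1.0 | 2 | 9.75 | 53.0% | 51.0% |
| 0.5 | 1 | 9.75 | 53.0% | 51.8% |
| 0.5 | 3 | 1.97 | 16.3% | 14.5% |

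Acrosssteps 1 and 2 the simulated rate runs from about 1% to 52%.

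**3. Does the missing pairing rule matter?** With equal pace, counts differ in 77% of simulated participants. Matching the first k or the last k intervals gives different verdicts in 3.5% of participants with no effect, and in 13% with a 1 s slowing. The expected proportion does not move: 49.0% v 49.2% at 1 s slowing, and 4.8% with no effect and independent intervals. An unpaired unequal-variance test per person does not help with the main problem: it flags 15.1% at ρ = 0.3 and 27.0% at τ = 0.5 s.

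**4. Run length.** For the same 1 s slowing, 49% are flagged with a 6-minute task, 41% with 5 minutes and 34% with 4 minutes.

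**5. Contrast between tasks.** With ρ = 0.3, τ = 0.5 s and 6-minute runs for both tasks, the two proportions agree under no effect (32.5% v 31.9%). They separate when only the technical task slows by 1 s (32% v 52%).

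**6. The alternative.** A paired t-test across 20 or 40 participants (assumed) on one mean or SD per run flags about 4% to 6% under no effect, over the same ρ and τ. This requires that run-to-run shifts average zero.

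If pace drifts by d seconds per run, control is run 1 and each task averages run 2.5, so a control comparison carries a mean shift of 1.5d. Take n = 20, τ = 0.5 s, ρ = 0. The variance of a participant's difference is 2 × 0.5² + 2 × 2²/35 + (0.5d)², which is 0.739 at d = 0.2 and 0.751 at d = 0.3.

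- Standard errors are √(0.739/20) = 0.192 and √(0.751/20) = 0.194.
- Shift over standard error is 0.30/0.192 = 1.56 and 0.45/0.194 = 2.32.
- From the noncentral t on 19 degrees of freedom, the false-positive rates are 32% and 60%.

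Administrative v technical, with balanced order, stays at about 4%.

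**The case against.** The strongest reply is that the plan may already intend the right analysis. Its individual-level bullet can mean pairing by individual across the group. Statistical methods supports this, and the normality check is motivated there by small sample size, which suits participants better than some 35 intervals per run. That stands as a reading of the first bullet, and a reader should not infer that the plan contains no valid timing test. It does not rescue the second bullet, which cannot be produced without a verdict on each person.

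A reader might also infer that the missing pairing is what distorts the proportion. Step 3 shows otherwise: it makes individual verdicts arbitrary but leaves the expected proportion unchanged.

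A further inference would be that the two proportions tell the reader nothing. That goes too far. Both use the same control run, and step 5 shows that their contrast keeps meaning when correlation, run-to-run variation and run length are similar in both tasks. The run-length worry needs one task to finish early systematically. The planned split into two-minute thirds suggests that most runs are expected to last about 6 minutes.

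Finally, all the magnitudes are assumed. They show what is possible, not what is likely. Individual differences in load do motivate the study, but they can be shown without p-values.

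**Conclusion.** The concern holds for the reported proportions. With no task effect, the share flagged could be near 1% or above 50%, depending on serial correlation, interval SD and run-to-run variation. The documents give none of these and the plan estimates neither the correlation nor the run-to-run variation. It would be wrong to say that the count must be inflated: negative correlation pushes it below 5%. What can be said is that neither proportion can be read as the share of clinicians affected.

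The inconsistent paired unit is a secondary fault of wording. Severity is modest: the plan describes itself as a hypothesis-generating pilot, this is one result among several, and the pedal timestamps are recorded, so reanalysis is possible.

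**What to change.** - In Time interval analysis and Statistical methods, state that the participant is the paired unit. Reduce each run to one value per participant, using the mean and the SD of intervals already derived.
- Apply the three planned paired comparisons across participants to those values, and apply the Shapiro-Wilk check to the between-run differences.
- Remove the per-person significance tests and the proportion built on them. Keep each individual's mean deviation from baseline, already listed, as a descriptive result.
- Make administrative v technical, whose order is randomised, the main timing comparison. Report the two control comparisons with the caveat that control is always first, so they also contain practice, fatigue and order effects.

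The cost is a few lines of wording, with no extra data or participants. The individual-level significance count is lost.

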However there is a key difference in the clinical populations found in the literature, surgeons have an operative team and are not responsible for patient monitoring while operating. Likewise anaesthetists are usually accompanied by an ODP and are not undertaking practical skills in isolation.

We were not able to find any published literature addressing attention and perception during ICU procedures.

What does this research add?

There is no published experimental data investigating how clinician time perception and attention are impacted by performing tasks in an IC environment. There is an expectation that time perception and attention are preserved, such that clinicians can insert central access as a sole practitioner. Should our investigation show that attention is impacted then this could inform changes to practice as to how monitors and/or additional staff members are utilised during procedures and clinical tasks and how practitioners are trained to undertake them.

AIM(S) OF STUDY

- To investigate the relationship between task type, perceptual loading and attention in an ICU environment
- To investigate the relationship between task type, perceptual loading and time perception in an ICU environment
- To examine if the extent of these effects (if any) are affected by clinician role and/or experience

OBJECTIVES

The objective of this study is to measure clinician awareness of time progression and monitoring trends in the clinical environment during 2 different types of task.

HYPOTHESIS

H₀: Task type has no impact on clinician time perception or awareness of monitoring trends.

H_A: In the technical task clinician time awareness is more inaccurate than in the administrative task

H_B: In the technical task clinician awareness of monitoring trends is impaired compared to in the administrative task

STUDY DESIGN

STUDY SETTING/LOCATION

This will be a single-centre study undertaken in the Intensive Care Units at Great Ormond Street Hospital. The study tasks will be run in the simulation room on the general Paediatric ICU.

STUDY POPULATION

Participants will be recruited from the group of ICU junior/senior tier fellows and Consultants working on the ICUs at Great Ormond Street Hospital. This comprises a pool of around 40 staff members. All staff members are routinely involved in the care of patients in a PIC environment.

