Participants will be recruited through convenience sampling of those working or training on the ICUs on days when it is possible to run the tasks. Individuals will not be recruited more than once.

Each participant will be given a numeric study ID and parameters recorded against this including:

- Job title- Consultant/fellow
- Gender- Male/female/prefer not to say
- Age- 21-30/31-40/41-50/51-60/61+
- Number of CVCs that they have previously inserted - <10, 10-50, >50).
- Time since last simulation training- 1 week/ 2-4 weeks/ 1-2 months / 3-6 months / 7-12 months / 1-2 years / >3 years

STUDY OUTCOMES

Primary Outcomes

Mean and standard deviation (accuracy) of time intervals measured.

Accuracy of retrospective recall of trends in monitored observations.

Secondary Outcomes

Impact of experience on time perception and monitoring changes.

STUDY PROCEDURES

Recruitment of participants

Participants will be provided with the information sheet appended and given the opportunity to ask any questions before consenting to the study. They will be asked to sign the appended consent form. Their consent forms will be in no way linked to the data collected such that participants could be identified from their data.

Randomisation

Block randomisation will be used to ensure even distribution of individuals at each grade of experience between the allocation groups. A block size of 4 will be used with 2 strata (grade= Consultant, Other). The randomisation list was determined by an online randomisation service ^[27]. The list generated is included as an appendix.

Two parts of the experimental process are randomised.

The first is the order in which the administrative and technical tasks are performed- this is randomised to remove the impact of primacy-recency impacts as well as task training through more practice with the timing apparatus.

The second is the scenario displayed on the monitor. As we are asking participants to identify a trend, randomisation to an increasing or decreasing trend reduces the likelihood of guessing the correct answer.

The study cannot be blinded at the time of data capture given the significant obvious differences between the tasks.

Study procedure

Structure

The overall structure is outlined below with further detail on each section provided in the following section.

Section order	Comment
Consent and discussion	To ensure valid consent and answer queries

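### As written, the exploratory comparison of pedal intervals by task order uses neither the control-run baseline nor the role stratum, and loses precision if that baseline correlates with the task runs

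*Combined protocol and SAP*

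**What the plan says.** In Study procedure, the Structure table gives the purpose of the timing control task: "To assess baseline time perception for each participant". Experimental scenarios fixes its place: "Each participant will undertake the timing control task first and then both the administrative and technical tasks". The control run lasts 6 minutes and uses the same pedal and the same 10-second target as the task runs.

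Under Randomisation, task order is allocated in blocks of 4 within two role strata (Consultant, Other). The aim given is to remove primacy-recency effects and the effect of practice with the timing apparatus. On the list in the appendix, each stratum has 10 administrative-first and 10 technical-first rows.

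Under Measurement tools used, the time interval analysis includes "Comparison of the mean perceived time interval between subgroups", split by task order, time within task, grade, number of CVCs inserted, and first versus last quarter of participants. The same list of results contains "Mean deviation for each individual from their baseline in each of the tasks".

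Under Statistical methods, the main timing comparisons are a "paired sample t-test for; control vs administrative, control vs technical and administrative vs technical". For subgroups the text reads: "For subgroup analysis paired or unpaired sample t-tests will be used as appropriate in each case". No ANCOVA, mixed model or stratum adjustment appears anywhere.

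**The concern.** Each participant has one task order. Comparing, say, the technical-task interval in those who did it first with those who did it second is therefore a comparison of different people, and of the tests offered only the unpaired one fits. Some people habitually press early and others late. In an unpaired test on the interval itself, those stable differences stay in the error term, although the control run has already measured them on the same scale.

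The control run is a sound covariate. It comes before both tasks, and before the break in which the first task is briefed, so task order should not influence it.

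At stake is the precision of the plan's check on whether a timing outcome depends on doing a task first or second. Numbers are small: "This comprises a pool of around 40 staff members", so at most about 20 people per order. An order effect is easier to miss, and its confidence interval wider, than the collected data may allow.

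**Working it through.** **Inputs.** The document gives no sample size, alpha, power, effect size, SD or correlation, so it has no figure of its own to reproduce. From the document: a pool of about 40 and 1:1 order allocation within role. Assumed: two-sided 5%; total N of 40 or 20 (20 or 10 per order); correlation rho between control-run and task-run mean interval from 0 to 0.7. Role was not modelled, so the results reflect baseline adjustment only.

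**Formulas**, with effects in SDs of the task-run mean interval:
- Unpaired t-test: variance factor 1, df = N - 2.
- ANCOVA on the control-run mean: variance factor (1 - rho²) × (1 + 1/(N - 4)), df = N - 3.
- Change from baseline: variance factor 2(1 - rho), df = N - 2, assuming equal SDs in control and task runs.
- Power from the non-central t, with non-centrality d / sqrt(4 × factor / N).

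**Variance factor at N = 40.** The small-sample term is 1 + 1/36 = 1.028.
- rho 0.3: 0.91 × 1.028 = 0.935
- rho 0.5: 0.75 × 1.028 = 0.771
- rho 0.7: 0.51 × 1.028 = 0.524

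At rho 0.5 the equivalent sample size is 40 / 0.771 = about 52. The unadjusted test then gives up precision worth about 12 people.

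**Power where the unpaired test has 80%:**

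| | rho 0 | rho 0.3 | rho 0.5 | rho 0.7 |
|---|---|---|---|---|
| 20 per order (0.91 SD), ANCOVA | 78.9% | 82.5% | 89.0% | 97.2% |
| 20 per order, change score | 51% | 66% | 80% | 95% |
| 10 per order (1.33 SD), ANCOVA | 77.3% | 81.0% | 87.8% | 96.6% |

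Starting from 50% power at rho 0.5, ANCOVA gives 60.7% (20 per order) and 59.0% (10 per order). In terms of the difference detectable with 80% power, ANCOVA breaks even at rho of about 0.17 (N = 40) and 0.26 (N = 20). Simulation agreed: at N = 40, rho 0.5 and an effect of 0.8 SD, the variance ratio was 0.78 and power 69% unadjusted against 80% adjusted.

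**An order effect common to both tasks.** Take each person's technical-minus-administrative difference. If the second run shifts the interval by p in either task, the two order groups differ by 2p on this difference, so p is half the group contrast. Assume equal variances and one common correlation rho for every pair of runs, with n per order:
- Within-person estimate of p: variance (1 - rho)/n.
- Per-task ANCOVA estimate: variance 2(1 - rho²)/n, before the small-sample term.
- Ratio: 1 / (2(1 + rho)), which is 1/3 at rho 0.5 and 1/2 at rho 0.

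At 20 per order and an effect of 0.64 SD, power at rho 0.5 is about 51% unpaired, 61% per-task ANCOVA and 98% within-person.

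**The case against.** **The test is inferred.** No sentence prescribes an unadjusted unpaired t-test for task order. That follows from the subgroup list, the wording on paired or unpaired tests, and order being a between-person factor. This stands as a limit on the wording. It does not remove the point, because the latitude given is between types of t-test and no covariate is provided for.

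**Baseline is used elsewhere.** Individual deviations from baseline are reported, but no between-order test of them is specified. A change score would also gain nothing at rho 0.5 and lose power below it, given equal SDs.

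**A within-person order test exists and is better.** Both orders are represented and everyone does both tasks, so an effect common to both tasks can be tested with the baseline cancelled and no covariate. This is right and shapes the fix. The document does not specify that test, however, and it does not answer whether one particular task's interval depends on its position.

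**Stronger readings the document does not support.** A reader might infer that the primary timing comparison is inefficient. It is not: it is paired, so the personal baseline cancels. A reader might also infer that order was randomised in order to test for an order effect. The stated purpose is to remove such effects by design. The comparison is one of five exploratory splits in a study described as a hypothesis-generating pilot.

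**The gain is not assured.** The protocol notes that people experience different loading from the same task, which could weaken the correlation between a resting run and a loaded one. This stands.

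**Conclusion.** The point holds in limited form. As the two sections read together, the between-order comparison of a task's mean interval leaves out a same-scale pre-task measurement and the randomisation stratum. It is a minor, optional improvement to an exploratory check, not an error in the main timing analysis.

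Its size rests on an unstated correlation. With 20 per order and two-sided 5%, the gain from 80% power is about 3, 9 and 17 points at rho 0.3, 0.5 and 0.7. If rho is 0, adjustment costs about 1 point at 20 per order and 3 at 10 per order. A moderate correlation is plausible for one person repeating the same pedal task within a session, but that is an assumption. The larger advantage of the within-person test applies only to an effect shared by both tasks, and its figures assume equal variances and correlations.

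**What to change.** Amend the time interval analysis and Statistical methods as follows.

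(a) For the technical or administrative interval in those who did that task first versus second, replace the unpaired t-test with an ANCOVA of task-run mean interval on task order, adjusted for the participant's control-run mean interval and role. Report the adjusted difference with its 95% CI.

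(b) For an order or practice effect common to both tasks, compare the two order groups on each person's technical-minus-administrative difference, or fit a mixed model with task, period and role.

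Leave the paired task contrasts as they are.

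The cost is a sentence or two and standard linear-model procedures. No new data are needed. ANCOVA uses one or two degrees of freedom, with the small power loss given above if the control run proves uninformative. Stating the model in advance also avoids a later choice between raw, change-score and adjusted results.
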